**Figure 8: The Plan-Prepare-Implement model for campaign development and community engagement**

Formative research activities for each campaign will follow a standard set of methods and procedures that also allow for each community to adopt campaign practices and messages that are best suited to their local context, the capacities and assets of their coalition, current perceptions of the opioid overdose challenges in the community by different priority groups, and any unique preferences for messages and communication channels. In at least three Wave 1 communities, the RS will conduct up to 5 focus groups or up to 25 individual interviews for message testing per campaign. The number of groups or interviews in each community will be dependent on the size of the community (i.e., smaller communities may require fewer focus groups than larger ones), the desired priority groups to recruit (i.e., some communities may choose to focus on one group; others may choose to focus a campaign on more), and how many groups or individuals per priority group are judged as necessary to validate results (one may be enough in some circumstances such as with coalition members or stakeholders; two to three may be needed for people with OUD or high-risk users, especially in larger communities). Each of these groups will be composed of up to 10 representatives from a stakeholder group (e.g., community leaders, public safety or criminal justice, health care providers, treatment centers) or priority population (e.g., people with OUD, family members, heroin users, high-risk patients or people from their social networks, people currently taking prescription opioids). We anticipate that up to 1,800 people across all HCS communities may be included in these focus groups, individual interviews, or research design workshops for each campaign (see the following moderator and facilitator guides: *Focus Group CAB, Coalition, and Partner*

*Organizations Guide; Focus Group for Persons with OUD; Focus Group Testing of Launch Messages; Communication Design Workshop Guide; Interview Guide Message Testing; Interview Guide Message Testing Persons with OUD), for an average of 54 participants per community.*

Throughout the campaign development process, we will test specific concepts and messages to express the theme in a way that is most relevant, compelling, and useful for the priority groups in each community. Appendix B contains the pool of items that we will pull from for these message testing and formative research activities. The community coalition, local partners, and their respective communication assets (e.g., community-hosted websites, social media pages, newsletters) will be a critical part of the campaign message dissemination process. In Table 5, we present more details about the key steps in the Prepare-Plan-Implement process.

**Table 5: Campaign Prepare-Plan-Implement process steps**

Prepare

 
1. Develop campaign guidebooks, campaign resources for coalitions, and messages materials.
 
2. Conduct a literature review and environmental scan of previous communication efforts around opioids and EBPs.             
 
a. Conduct a literature review and environmental scan of previous campaigns.
 
b. Extract data collected in the LA and qualitative interviews with coalition members to understand what communication assets and capabilities are available in communities to design, produce, and implement a communication campaign.
 
c. Conduct interviews with media representatives.
 
d. Perform online searches and seek information from the LA (asset mapping) and interviews with coalition leaders to learn about state or local communication efforts (previously conducted and currently on the ground); capture lessons learned from previous campaigns and note potential “competing messages” from current efforts.
 
 
 

Plan

 
1. Conduct up to five focus groups or up to 25 individual interviews for message testing groups in at least three Wave 1 communities with key stakeholders and/or representatives of priority groups for these interviews, focus groups, and design workshops (see Focus Group for Persons with OUD; Focus Group CAB, Coalition, and Partner Organizations Guide; Focus Group Testing of Launch Messages; Communication Design Workshop Guide; Interview Guide Message Testing Persons with OUD; and Interview Guide Message Testing).
 
2. Introduce campaign objectives, proposed priority groups, message materials, and findings from message testing and development timeline to community coalitions (via in-person or virtual meetings/presentations); solicit input and refine.
 
3. Introduce communication product ideas to each coalition; solicit input and refine ideas (e.g., social media copy, advertisements, sample op-eds, infographics).
 
4. Decide on message dissemination strategies and tactics with coalitions.
 
5. Articulate the implementation plan and review collaboration and integration touchpoints with CE and ORCCA teams.
 

6. Develop an implementation plan with the coalition including timelines, responsibilities, and milestones.
Implement

 
1. Coordinate release of first messages in the community (media choices to be determined via Landscape Analyses and media asset analyses) with kickoff events in each community.
 
2. Assist (where necessary) each community with selecting, using, and placing messages via previously selected/agreed-upon channels.
 
3. Engage partners to release campaign social media posts.
 
4. If placing paid advertisements (not required across communities), monitor advertisement placement and reach.
 
5. Hold monthly monitoring and feedback meetings of coalition/community implementation staff and RS.
 
6. Monitor social media and traditional media coverage of stories/trends surrounding naloxone, OUD, and MOUD.
 
7. Use monitoring data to make corrections to campaign implementation strategies/protocol and messages in each community (measures of campaign outputs including primary content, number and frequency of social media posts, advertisements, and earned media placements; feedback from coalition members and other community stakeholders).
 

In summary, the communication campaign will start from an HCS-produced campaign guidebook and message maps that will be taken to each community coalition for discussion, refinement, testing, and implementation. Although core objectives and messages will be common across Wave 1 communities, there are opportunities for coalitions to refocus priority groups and co-create the strategies and tactics later in the campaign that will be empty in the final implementation plan. The campaign schedule for the entire intervention period, across both waves of communities and including each phase of the Prepare (for Wave 1), Plan, and Implement process, is summarized in Table 6a for Wave 1 and 6b for Wave 2.

**Table 6a: Timeline for Stages of Communication Campaigns (Wave 1)**

Stage	Naloxone Campaign Wave 1	Stigma Campaign Wave 1	MOUD Campaign Wave 1	Stay in Treatment Campaign Wave 1	Community/Coalition Choice Wave 1	
Prepare	Sep 2019–Feb 2020	Sep 2019–Mar 2020	Sep 2019–Apr 2020	Nov 2020 – Apr 2022	Aug 2021 – Oct 2021	
Plan with coalition	Feb–Apr 2020	Apr–Jun 2020	Sep–Nov 2020	Apr 2021 – Jun 2021	Oct 2021 – Dec 2021	
Implement	Apr–Jul 2020	Jul–Nov 2020	Oct 2020 – May 2021	Jun 2021 – Dec 2021	Jan 2022 – May 2022	

**Table 6b: Timeline for Stages of Communication Campaigns (Wave 2)**

Stage	Campaign 1	Campaign 2	Campaign 3
Plan with coalition	Aug-Sept 2022	Jan-Feb 2023	Jun-Jul 2023
Implement	Oct 2022 – Feb 2023	Mar-Jul 2023	Aug-Dec 2023

Note, all campaigns were prepared during Wave 1. Each Wave 2 community will choose three of the four campaigns developed during Wave 1 (Naloxone, Stigma, MOUD, Stay in Treatment) to implement in three of separate campaign periods.

#### ***Overview of the HCS Communication Campaign Evaluation Study (HCS-CES)***

Given the investment in health communication campaigns as a pillar of the HCS, a rigorous scientific evaluation is proposed across the 67 HEALing communities of the four RSs. Central to this evaluation is a cross-sectional, repeated-measure, longitudinal community-level measurement of the attitudes, intentions, and perceptions of EBPs to prevent and treat OUD among the recipients of the campaign in HCS communities. Furthermore, the evaluation will measure the impact of the health communication messages for persuading individuals to seek out EBPs for OUD and the campaign's impact on reducing stigma surrounding OUD, OEND, and MOUD. All data collection points in the evaluation will coincide directly with the campaign activities for each wave of the HCS, allowing for rigorous measurement of impacts at the community level and among the recipients of the campaign in the HCS communities. Campaign evaluations are also necessary to guide mid-course adjustments of strategies and tactics and arrive at sound, evidence-based recommendations for the use of campaigns to address opioid and other substance use epidemics.

The **HCS-CES** therefore has three primary components:

1. A tracking study of the impact of HCS messages through daily monitoring and analysis of message dissemination activities and citizen exposure to them. The tracking study will also measure responses to action steps contained in the messages (i.e., community-specific URLs directing users to the HCS campaign webpage on the HCS website). Time-series analyses will be used to detect dose-response associations between the level of campaign activity and audience information-seeking on the HCS campaign webpage.
2. Monitoring of other opioid-related communication campaigns sponsored by state and national organizations will document other sources of information that residents of HCS communities may have been exposed to during the CTH intervention. Salient and frequent messages from one or more of these external campaigns may be incorporated into the longitudinal surveys to assess their recognition relative to the HCS campaign materials.
3. Survey data collection of community residents to assess changes in specific components of stigma toward individuals with OUD, the acceptability of naloxone

(OEND), and the acceptability of MOUD treatment in the Wave 1 and Wave 2 communities (see Figure 9 for a timeline and visual representation of data collection points for the HCS-CES community surveys). Survey data will be collected from a sample generated from social media recruitment (Facebook). In addition, participants may opt in to be part of a longitudinal panel in which they are surveyed at each time point. These changes will be assessed across communities using differences between treatment and control communities and within communities over time by dose-response effects associated with exposure to campaign messages and other messages in the community environment. See *Campaign Evaluation Questionnaire*.

### **HCS-CES Research Hypotheses**

- H1: Time-series analyses of tracking data will indicate positive associations between higher levels of message dissemination activities and audience information-seeking on the website.
- H2: The number of campaign messages correctly recognized, and the reported frequency of exposure to these messages, will be positively associated with desired attitudinal outcomes regarding stigma, naloxone distribution, and MOUD treatment at the individual respondent level.
- H3: In intervention communities receiving the health communication campaigns, self-reported stigma toward individuals with OUD will decline, and acceptance of EBPs will increase significantly over time at the community level.
- H4: In intervention communities receiving the health communication campaigns, self-reported awareness and acceptance of MOUD and OEND at the community level will significantly increase over time.

Because components 1 and 2 of the HCS-CES do not involve human subjects or collection of personally identifiable information (PII), the rest of the discussion of the HCS-CES will focus on the third component: the survey data collection of community residents. There will be seven data collection phases:

- (1) CEQ1: March-April, 2020, Wave 1 and 2 communities (baseline)
- (2) CEQ2: September-October, 2020, Wave 1 only (post-Campaign 1)
- (3) CEQ3: January-February, 2021, Wave 1 only (post Campaigns 2 and 3)
- (4) CEQ4: May-June, 2021, Wave 1 and Wave 2 (pre-Campaign 4 and beginning of CTH evaluation phase, secular trends comparison in Wave 2)
- (5) CEQ5: November-December, 2021, Wave 1 only (post-Campaign 4)
- (6) CEQ6: May-June, 2022, Wave 1 and Wave 2 (post Campaign 5, CTH evaluation phase comparison)
- (7) CEQ7: May-June, 2023, Wave 1 and Wave 2 (Campaign effects in Wave 2, sustainability comparison in Wave 1)

## Community Survey Participants

The study population for the HCS-CES community surveys will include any community member older than age 18 who resides in one of the 67 HCS communities. These individuals will be recruited for the campaign evaluation surveys via a series of Facebook/Instagram advertisements targeted to people aged 18 or older who reside within the ZIP Codes of the 67 communities. Data from the Health Information National Trends Survey demonstrates that social media is an effective tool for health communication research. Specifically, researchers have found Facebook to be a viable platform for recruiting participants from lower socio-economic backgrounds, recruiting representative samples, and contacting hard-to-reach populations. Using Facebook is also a cost-effective recruitment strategy. Additionally, Healthy People 2020^56 has demonstrated the reach and penetration of mobile device data plans and found no significant difference in accessing Internet via cellular networks on the basis of rural versus urban communities, gender, Hispanic and non-Hispanic populations, and educational attainment. Recruiting via social media has become an increasingly popular method for conducting surveys, because recruitment for telephone surveys has become increasingly challenging.

Prior to completing the pre-test survey (more details below in the HCS-CES procedures section), participants from Facebook/Instagram samples will be asked to complete a brief two-minute screening survey. Respondents will be routed to a screening survey that RTI has programmed in the Qualtrics survey system. RTI's license includes the premium data isolation feature, meaning the data are encrypted at rest. As a part of the screener, participants will be asked to provide their email address. For this question, the participant will be directed to a separate instrument so that the email address is stored within the Qualtrics system but separately from the other screener questions. Responses to screening questions will also be kept separate from the pre-test, intermediate, and post-test survey data since these data will be hosted on REDCap (more details below). This screening survey will be completed by each new sample obtained for subsequent campaigns.

The Qualtrics survey system has advanced capabilities to monitor the screening success rates, and to prevent fraudulent activity that is pervasive during social media survey recruitment. Using Qualtrics allows the study to implement best practices for social media survey respondent recruitment.

Respondents deemed eligible for the survey based on responses to the screener will be routed to a REDCap survey. Upon completion of the pre-test, intermediate, or post-test surveys, participants will be offered the opportunity to enter a drawing to win a \$100 Amazon electronic gift card. One electronic gift card will be distributed to one winner in each of the 67 communities per data collection period. Those individuals wishing to enter the drawing will be offered the opportunity to voluntarily enter their name and email address at the end of the survey, so they can be contacted if they win the gift card.

The primary analysis is to assess the average stigma change in communities with the campaign. We expect to see a mean change score of at least 0.05. Furthermore, based on pilot data from Maulik, Siddhardha, Sudha, Abha, Shailaja, Miria, and Thornicroft (2017), we assume a SD of 0.09 for paired changes. However, our data are collected cross-sectionally, and therefore the SD corresponding to changes from pre to post will be larger. To be conservative with our sample size calculations, we assume a very large correlation of 0.95 for

pairs, which maps the 0.09 SD to a conservative SD of 0.40 for our cross-sectional study. Furthermore, we calculate required numbers of surveys per community corresponding to intra-cluster correlation coefficient (ICC) values ranging from 0.01 to 0.05, which statistically account for differences in mean changes across the communities. Based on these conservative assumptions, we will need approximately 20 to 80 surveys per community, on average, to be completed at each time point for each of the 33 Wave 1 communities in order to have at least 80% power for a two-sided test at the 0.05 significance level. With respect to baseline data for Wave 2, if we collect the same number of surveys across these 33 other communities, then these assumptions imply we will be able to estimate the true mean stigma score within +/- 0.024, based on a 95% confidence interval.

Data collection for each time point in the REDCap survey will be programmed to continue until this number of desired completions has been achieved. If a participant elects to not volunteer for future surveys or enter the raffle, all surveys will be anonymous. We will not be collecting any PII other than basic demographics (age, gender, race/ethnicity, educational attainment, and whether they self-identify as a health care provider or community leader). If participants elect to volunteer for future surveys, the raffle, or both, their information (name and email address) will remain confidential and will be used only for purposes of contacting for future surveys or informing them that they won a raffle.

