#### Details of proposed survey of attitudes regarding stigma, naloxone availability, and MOUD for each discrete campaign

***Campaign Evaluation Questionnaire:*** For the proposed community survey, the Facebook advertisements will target individuals living in the geographic regions of all 67 HCS communities. The survey will be programmed to continue until the number of desired completions has been achieved. Each discrete CEQ will be staggered to serve as both pretest for the beginning campaign and posttest for each previous campaign as test messages from all previous campaigns will be iteratively added to each subsequent CEQ. This will provide an overall impression of message recognition from each previous campaign (via cued recall of messages used in each previous campaign) as well as the current campaign.

The CEQ includes measures of stigma toward individuals with OUD and EBPs to prevent or treat OUD, as well as awareness and intentions to seek MOUD and OEND. Using a cued-recall survey methodology (discussed as follows), respondents will also be asked questions about recognition and attitudes toward other competing campaign messages being disseminated in their community. They will not be shown HCS messages at baseline. Survey completion is estimated to require approximately 20 minutes. Individuals will be asked if they are willing to be

re-contacted for the second and third time points of the campaign currently running in their community, and if willing, to provide an email address to help construct the cohort panel discussed previously. This process will be duplicated for all subsequent Campaign Evaluation Questionnaires.

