1	Purpose	Survey data for evaluation of the health communication campaigns within and across all four HCS sites
2	Respondent	Community members
3	How will respondents be selected?	Via targeted Facebook advertisements seeking respondents in their respective communities to take the survey evaluating the campaign
4	Sample size	In total, across all 4 sites and all campaigns of the HCS, approximately 30,000 surveys will be completed
5	Repeated (Y/N)	Yes
	If yes: frequency (e.g., annually, monthly)	3 times for each campaign (as a pre-test, intermediate, and post-test) for 6 campaigns (Wave 1 and Wave 2) plus additional baseline and post-tests * 4 sites = 84 times repeated
6	Mode (telephone, web, in person)	Web
7	Self-administered or interviewer administered	Self-administered. Interested respondents will click a Facebook advertisement that will take them to the REDCap survey where they will read and consent to participate, then they will begin the survey and complete it online via REDCap
8	Informed consent (verbal, written, digital)	Digital
9	Incentives (Y/N)	Yes
	If yes: incentive type (e.g., gift card, cash, check)	A raffle of a \$100 Amazon e-gift card for each survey time point for each county or community participating in the survey at that time
10	Seeking Waiver of Documentation of Informed Consent (Y/N)	Yes
11	Cross-site or site specific (specify site)	Cross-site

12	Data collection platform (e.g., paper, REDCap, video)	REDCap
13	Audio-recording (Y/N)	No
14	Other respondent-facing material (e.g., email invitation to participate) (specify)	N/A

Coalition Meeting Minute Template		
Main Study Data Collection		
1	Purpose	To assess adherence and quality of implementing the CTH intervention
2	Respondent	HCS research staff
3	How will respondents be selected?	HCS research staff hired by the study
4	Sample size	67
5	Repeated (Y/N)	Yes
	If yes: frequency (e.g., annually, monthly)	Will vary; dependent on how often the coalition meets
6	Mode (telephone, web, in person)	In person or web
7	Self-administered or interviewer administered	Self-administered
8	Informed consent (verbal, written, digital)	N/A
9	Incentives (Y/N)	No
	If yes: incentive type (e.g., gift card, cash, check)	N/A
10	Seeking Waiver of Documentation of Informed Consent (Y/N)	No

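### The campaign evaluation names the uncontrolled Wave 1 stigma change as its primary analysis and gives power only for that; the planned Wave 1 versus Wave 2 comparison is not primary, has no fixed rounds or model, and has no stated power.

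*Protocol*

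**What the plan says.** All protocol text on this point is in Section 6.1.1.4 unless noted.

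- **Analysis named primary** (Community Survey Participants): "The primary analysis is to assess the average stigma change in communities with the campaign". The expected mean change is at least 0.05. About 20 to 80 surveys per community per time point, in 33 Wave 1 communities, are required "in order to have at least 80% power for a two-sided test at the 0.05 significance level".
- **Wave 2** (same paragraph): "With respect to baseline data for Wave 2, if we collect the same number of surveys across these 33 other communities", then "we will be able to estimate the true mean stigma score within +/- 0.024, based on a 95% confidence interval". This is the only figure given for Wave 2. It is conditional, and it concerns the precision of the baseline mean.
- **Hypotheses** (HCS-CES Research Hypotheses): H3 reads "In intervention communities receiving the health communication campaigns, self-reported stigma toward individuals with OUD will decline". H4 is likewise a change over time within intervention communities.
- **Controlled comparison**: component 3 of the HCS-CES overview says changes will be assessed by differences between treatment and control communities, and by dose-response within communities. The list of survey rounds includes both waves at CEQ1 (baseline), CEQ4 (with a secular-trend purpose for Wave 2), CEQ6 (May-June 2022, described as an evaluation-phase comparison) and CEQ7. HCS-CES Procedure adds Wave 2 annually for comparison.
- **Survey numbers**: "Data collection for each time point in the REDCap survey will be programmed to continue until this number of desired completions has been achieved"; "the Facebook advertisements will target individuals living in the geographic regions of all 67 HCS communities"; and in Table 10, "In total, across all 4 sites and all campaigns of the HCS, approximately 30,000 surveys will be completed".

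The SAP supplied is limited to opioid overdose deaths and does not cover the campaign surveys.

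**The concern.** A within-arm change from CEQ1 to a later round contains the campaign effect plus anything else that moved attitudes in that period. The protocol expects such influences: it monitors outside campaigns, shows respondents a non-HCS message and a foil, and gives CEQ4 a secular-trend purpose. The randomised Wave 2 communities are surveyed at CEQ6, before they start the intervention in July 2022, so the data that would remove a common shift are already scheduled. The analysis named primary does not use them.

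Two things are at stake. A shift shared by both waves could be reported as a campaign effect. And a reader could carry the 80% power over to the between-wave comparison, for which it was not calculated.

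**Working it through.** **Inputs** (Protocol, Community Survey Participants): effect 0.05; SD of paired changes 0.09; pair correlation 0.95; cross-sectional change SD 0.40; ICC 0.01 to 0.05; m = 20 to 80 surveys per community; K = 33 communities; two-sided 0.05. The two ends are m = 20 with ICC 0.01 and m = 80 with ICC 0.05.

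**1. Reproduce the SD.** Level SD = 0.09/√(2 × (1 − 0.95)) = 0.2846. Change SD = 0.2846 × √2 = 0.4025 (protocol: 0.40).

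**2. Reproduce the power.** Design effect D = 1 + (m − 1) × ICC = 1.19 and 4.95. One-arm SE = 0.40 × √(D/(33m)) = 0.01698 and 0.01732. Noncentral t on 32 df gives power 0.814 and 0.799 for 0.05. So 20 to 80 surveys is the requirement for a test without a control arm.

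**3. What that test responds to.** Smallest significant mean change = 2.037 × SE = 0.0346 and 0.0353. The documents give no size for a shared shift. As assumptions only, with no campaign effect:

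| Assumed shift common to both waves | Chance of a significant result |
|---|---|
| 0.01 | 0.088 and 0.087 |
| 0.025 | 0.298 and 0.288 |

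**4. Does the ICC range apply to levels?** For one wave's mean, 1.96 × 0.2846 × √(D/(33m)) = 0.0237 and 0.0242, matching the stated 0.024. Without the ICC it would be 0.0217 and 0.0109. The protocol's own precision figure therefore needs the ICC on levels, although its wording ties the ICC to differences in mean changes.

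**5. CEQ6 level contrast, 33 versus 33, equal numbers.** SE = 0.2846 × √(2D/(33m)) = 0.01709 and 0.01743. On 64 df, power is 0.822 and 0.807 for 0.05; the 95% CI half-width is 0.0341 and 0.0348.

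**6. Difference in change, and CEQ1 adjustment.** Let r be the correlation of a community's underlying level between rounds (not given in the documents). The variance of a community mean is V = 0.2846² × (ICC + (1 − ICC)/m), and the covariance between rounds is C = 0.2846² × ICC × r. The difference in change has SE = √(2 × (2V − 2C)/33). The CEQ1-adjusted contrast has approximately SE = √(2V × (1 − (C/V)²)/33).

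| r | Difference in change: m=20, ICC 0.01 | Difference in change: m=80, ICC 0.05 | CEQ1-adjusted: m=20, ICC 0.01 | CEQ1-adjusted: m=80, ICC 0.05 |
|---|---|---|---|---|
| 0 | 0.53 | 0.52 | 0.82 | 0.81 |
| 0.5 | 0.57 | 0.74 | 0.82 | 0.87 |
| 0.8 | 0.59 | 0.92 | 0.83 | 0.96 |

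With the protocol's rounded SD of 0.40, the r = 0 figures for difference in change are 0.54 and 0.52. At every r tried, the CEQ1-adjusted contrast has more power than the difference in change.

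**7. Are equal Wave 2 numbers plausible?** The round list has 7 Wave 1 and 4 Wave 2 rounds. 33 × (7 + 4) × 80 = 29,040, close to Table 10's total of about 30,000. Wave 2 at baseline only would give 33 × 8 × 80 = 21,120. Table 10's own repeat count (84) does not match seven rounds, so this is a consistency check only.

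**The case against.** The strongest reply is that the protocol already plans a controlled comparison. Component 3 names the type of contrast (changes, treatment versus control), CEQ4 has a secular-trend purpose and CEQ6 is an evaluation-phase comparison. That stands. A reader might infer that the evaluation has no controlled comparison, or that its contrast is wholly unspecified; the documents do not support either reading. What is missing is its status as primary, its rounds, its model and its power.

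A reader might also infer that the difference in change has a design power of only 0.52 to 0.54. That holds only if community levels are uncorrelated between rounds; at ICC 0.05 and r = 0.8 it is 0.92. It should not be quoted as a single figure.

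Nor can one conclude that no campaign analysis plan exists. The supplied SAP was narrowed to opioid overdose deaths (SAP Section 1.3), and Protocol Section 9.4.6 refers the comparison group in some analyses to a statistical analysis plan. Details may sit in a document not supplied.

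Outside-campaign monitoring, the foil and dose-response analysis help to interpret exposure effects. They do not subtract a common shift from a within-arm mean change. The CEQ4 comparison could reveal such a shift, but nothing says that it would correct the analysis named primary.

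**Conclusion.** The point holds for the campaign evaluation. On the supplied text, the analysis labelled primary is an uncontrolled Wave 1 change, its 80% power belongs to that contrast alone, and a shift common to both waves would be counted as a campaign effect. The test reaches significance at a mean change of about 0.035, whatever the cause. How much bias this produces is unknown, because the documents give no shift size.

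The scheduled randomised contrast at CEQ6 costs little power: about 0.81 to 0.82 for 0.05 unadjusted. This assumes equal Wave 2 numbers, 33 communities per wave, and the stated ICC range applied to score levels. The trial's primary outcome, opioid overdose deaths, is not affected. This is a change that should be made, with medium confidence because a separate campaign plan may exist.

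**What to change.** In Community Survey Participants, and in H3 and H4:

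- Rest any claim of a campaign effect on Wave 1 versus Wave 2 community scores at CEQ6, adjusted for the CEQ1 community score and the randomisation factors. Show the unadjusted contrast beside it, because CEQ1 (March-April 2020) ends in the month Campaign 1 starts (Tables 4 and 6a).
- Say that this estimates the effect of CTH including its campaigns, since the waves differ in the whole intervention.
- Label the within-Wave-1 change as descriptive and uncontrolled.
- Say how the withdrawn Wave 1 community is handled: SAP Section 3.1 has 34 randomised, SAP Section 6.2.5 records one withdrawal after randomisation, and the survey sample size counts 33.
- State that the 80% power applies only to the one-arm change. If power is given for the CEQ6 contrast, give about 0.81 to 0.82 for 0.05 unadjusted, with its assumptions. For a difference in change, give a range by between-round correlation: about 0.52 to 0.54 with none, rising at 0.8 to about 0.59 (ICC 0.01) and 0.92 (ICC 0.05).
- Report realised survey numbers by wave at CEQ1 and CEQ6, with the confidence interval.
- If the CEQ6 data have been examined, declare the change of primary contrast as post hoc.

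The cost is wording, one power statement and one table; no new data are needed. The last round was scheduled for May-June 2023 and the latest amendment in the protocol history is dated March 2025, so prespecification may already be lost.
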